3.5. Patient Completion

Patients who participate in the study in compliance with the protocol for 36 weeks of OL treatment will be considered to have completed the treatment period. Patients who complete the

EOS visit (week 51) will be considered as having completed the study. See Section [3.6](#) for the definition of the end of the study.

3.6. End of the Clinical Study

Last Patient Last Visit (LPLV) of the treatment period is defined as the EOT. The EOS visit for immunogenicity testing only will be performed 19 weeks (± 2 weeks) after the final dose of study drug (approximately week 51). This will be considered the end of the trial for the purposes of end of trial notification.

3.7. Schedule of Study Procedures and Assessments

Study procedures and assessments with their time points are presented in [Table 1](#). Detailed descriptions of each method of procedures and assessments are provided in Section [6](#) (efficacy assessments), Section [7](#) (safety assessments), and Section [8](#) (other assessments). Study procedures and assessments by visit are listed in [Appendix B](#).

Table 1: Study Procedures and Assessments

Study period	Screening		Open-label treatment period											
Visit number	V0 ^a Screening for non- seam- less enrollees	Run-in for non- seam- less enrollees	V1 ^a Screening /baseline	V2	V3	V4	V5	V6	V7	V8	V9	V _{EOT} EOT or early with- drawal	V _{FU} Follow-up telephone assessment	V _{EOS} EOS
Procedures and assessments	W-2 -14d to ≤-7d	-7d to 0d	W0	W4 ±7d	W8 ±7d	W12 ±7d	W16 ±7d	W20 ±7d	W24 ±7d	W28 ±7d	W32 ±7d	W36 ±7d	W48 (EOT +12W) ±14d	W51 (V9 +19W) ±14d
Informed assent/consent	X		X											
Medication history	X		X											
Inclusion and exclusion criteria	X		X											
Pregnancy testing	X ^b		X ^c	X	X	X	X	X	X	X	X	X	X	
Hematology (CBC with differential) (prior to IMP administration)	X		X ^c		X				X			X		
Serum chemistry tests with CPK ^d (prior to IMP administration)	X		X ^c	X	X				X			X		
Blood for ADA ^e			X ^c		X				X			X		X
Full physical examination ^f	X		X ^c									X		
ECG ^f	X		X ^c									X		
Vital signs ^f	X		X ^c	X	X	X	X	X	X	X	X	X		
Height and weight	X											X		
Pre-bronchodilator spirometry ^g			X ^c		X				X			X		
ACQ-6			X ^c		X				X			X		
AQLQ12+			X ^c		X				X			X		

Table 1: Study Procedures and Assessments (Continued)

Study period	Screening		Open-label treatment period											
Visit number	V0 ^a Screening for non- seam- less enrollees	Run-in for non- seam- less enrollees	V1 ^a Screening /baseline	V2	V3	V4	V5	V6	V7	V8	V9	V _{EOT} EOT or early with- drawal	V _{FU} Follow-up telephone assessment	V _{EOS} EOS
Procedures and assessments	W-2 -14d to ≤-7d	-7d to 0d	W0	W4 ±7d	W8 ±7d	W12 ±7d	W16 ±7d	W20 ±7d	W24 ±7d	W28 ±7d	W32 ±7d	W36 ±7d	W48 (EOT +12W) ±14d	W51 (V9 +19W) ±14d
Assess asthma control including asthma exacerbations and related HCU: step-down background medication (eg, OCS) if clinically appropriate ^h	X		X ^c	X	X	X	X	X	X	X	X	X		
Provide/collect handheld electronic diary/spirometry device; reinforce diary and PEF/spirometry compliance	X		X	X	X	X	X	X	X	X	X	X		
Patient daily use of handheld electronic diary/spirometry device		X											→	
Adverse event inquiry	X		X ^c	X	X	X	X	X	X	X	X	X	X	
Concomitant medication inquiry ⁱ	X		X ^c	X	X	X	X	X	X	X	X	X	X	
IMP administration			X	X	X	X	X	X	X	X	X			
Injection site assessment ^j			X	X	X	X	X	X	X	X	X			

^a Visit 1 (screening/baseline) will take place at the EOT visit for patients seamlessly rolling over from Studies 30025 and 30027. Any patient who did not rollover seamlessly from Study 30025 or 30027 will be seen first at an earlier screening visit (V0) in order to complete informed consent and eligibility criteria procedures before completing all other procedures and IMP administration at V1. Adolescents (a patient 12 through <18 years of age) from Study 30025 can complete the V0 screening visit of Study 30066 the same day as the 12 week early follow up visit for Study 30025. Additionally, any patient who did not rollover seamlessly from Study 30025 or 30027 will participate in a 7-day run-in period where baseline measures for asthma control and spirometry will be established. The screening period (including run in) will be up to a maximum of 14 days. Patients who complete the screening assessments of informed assent/consent, medication history, and inclusion and exclusion criteria at V0 do not need to repeat them at V1. Any assessments that are performed at V0 do not need to be repeated at V1 if completed within the previous 14 days (including blood tests completed by adolescents at the 12 week early follow up visit for Study 30025).

Clinical Study Protocol

Open-Label Extension Study—Eosinophilic Asthma Study C38072-AS-30066

^b Beta-human chorionic gonadotropin serum pregnancy tests will be performed at V0 for patients who did not seamlessly rollover (female patients who are not postmenopausal or surgically sterile only). Urine pregnancy testing will be performed at all other visits for all female patients who are not postmenopausal or surgically sterile only. Note: FSH level will be obtained from serum chemistry test as required to determine postmenopausal status. Please see the Laboratory Manual for further information.

^c These assessments may have been done as part of the EOT visit of Study 30025 or 30027 if patient seamlessly enters open-label study.

^d If a potentially clinically significant CPK level ($\geq 3.1 \times$ ULN) occurs, please refer to Protocol Section 7.1.6.1.2 for further management.

^e For ADA collection, a blood sample will also be collected in the event of withdrawal from the study or upon observation of any severe hypersensitivity reaction (eg, anaphylaxis). An unscheduled sample can also be drawn after a serious adverse event if the investigator or sponsor considers appropriate. When applicable, blood samples for ADA should be taken before drug administration. Reslizumab concentration data will be assessed from the ADA blood samples.

^f The “full” physical examination should include the following organ systems: general appearance; head, eyes, ears, nose, and throat; chest and lung; heart; abdomen; musculoskeletal; skin; lymph nodes; and neurological. Physical examination, ECG, and vital signs (includes systolic and diastolic blood pressure, pulse, body temperature, and respiratory rate) should be obtained before spirometry procedures and IMP administration. If screening occurs over multiple visits, vital signs at minimum should be performed at the initial screening visit and repeated on the day of V1.

^g Pre-bronchodilator spirometry assessments at designated clinic visits (weeks 0, 8, and 24, and EOT) should only be performed after withholding short-acting bronchodilators (ie, inhaled short-acting beta-adrenergic agonists and/or short-acting anticholinergics) for at least 6 hours and long-acting bronchodilators (ie, inhaled long-acting beta-adrenergic agonists and long acting anticholinergic agents) for at least 12 or 24 hours, according to their labeled dose schedule.

^h Investigators can reduce maintenance OCS as clinically indicated.

ⁱ Inquiry will include assessment of OCS dose if participants are on maintenance corticosteroids.

^j Assessment should be made approximately 1 hour after study drug administration.

ACQ-6=Asthma Control Questionnaire; ADA=anti-drug antibody; AQLQ12+=Asthma Quality of Life Questionnaire; CBC=complete blood count; CPK=creatine phosphokinase; d=day; ECG=electrocardiogram; EOS=end of study; EOT=end of treatment; FSH=follicle stimulating hormone; FU=follow-up; HCU=healthcare utilization; HCG= human chorionic gonadotropin; IMP=investigational medicinal product; OCS=oral corticosteroid; PEF=peak expiratory flow; PI=principal investigator; ULN=upper limit of normal; V=visit; W=week

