9.1. Sample Size and Power Considerations

The sample size for this OL extension study is not based on power considerations. The sample size is determined by the number of patients anticipated to rollover from the 2 double-blind, placebo-controlled, Phase 3 studies of reslizumab sc (Studies 30025 and 30027).

Approximately 360 patients will be enrolled in this OL extension study. The objective of this study is primarily safety oriented; therefore, no formal hypothesis testing is planned. Patients completing at least the full treatment periods of Studies 30025 and 30027 (or through at least the early follow-up visit for adolescents from Study 30025) and meeting the protocol's inclusion criteria and none of the exclusion criteria are eligible for enrollment in this study. It is estimated that the majority of patients enrolled in eligible reslizumab safety and efficacy studies will rollover to this OL extension study.

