APPENDIX J. ASTHMA CONTROL DIARY (ELECTRONIC DIARY)

(Sample provided in this appendix is for reference only.)

Handheld Spirometer

- You will need to perform your forced expiratory volume in 1 second (FEV₁) and peak expiratory flow (PEF) reading every morning using the handheld spirometer.
- You will need to perform your PEF every evening using the handheld spirometer.
- Blow into your handheld spirometer 3 times in the morning and 3 times in the evening.

Rescue Medication (Do not record SABA use for exercise pretreatment!)

Total number of puffs (daily):

[figure not shown]
Symptoms Post-injection:

[figure not shown]
- Have you received a study medication injection within the last 24 hours?
- Have you experienced any new symptoms since the study drug injection?

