#### 4.2.1. Diary

Baseline for diary-based efficacy variables (total reliever bronchodilator medication, █) will be defined as the average of the values over the 7 days preceding the first dose of reslizumab in this study. At least 4 out of the 7 expected measurements need to be recorded for each diary variable; otherwise the baseline value for that variable will be treated as missing. This definition will exclude daily morning ambulatory FEV1 whose baseline value will be derived as outlined in Section 4.2.2.

For non-seamless rollovers, baseline will be derived from data collected in this study during 7-day run-in period prior to Visit 1. For seamless rollovers, baseline will be derived from data collected during the 7 days preceding the EOT visit of the previous study (30025 or 30027).

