#### 4.2.2. Spirometry

Pre-bronchodilator FEV1 at pre-specified clinic visits and daily morning ambulatory FEV1 will be measured using a handheld device that has combined spirometry and eDiary capabilities.

The baseline value for pre-bronchodilator FEV1 measured at the clinic visits will be the last observed value prior to the first dose of reslizumab in this study. The baseline value for daily morning ambulatory FEV1 will be defined similarly.

For non-seamless rollovers, baseline will be derived from data collected in this study on or prior to Visit 1. For seamless rollovers, baseline will be derived from data collected at the EOT visit of the previous study (30025 or 30027).

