#### **6.3.2.2. Analysis**

Summary statistics of actual values and changes from baseline to each scheduled visit in pre-bronchodilator FEV1 measured using spirometry will be provided by previous double-blind treatment group and for all patients. A line graph presenting the mean change from baseline over time (at each visit) will be provided for prebronchodilator FEV1 by previous double-blind treatment group.

A weekly average of daily morning ambulatory FEV1 (measured by the handheld spirometry device) will be derived using 7-day window intervals based on these analysis days (see Table 1 for the definition of analysis days for diary data). The average will be calculated as the sum of all values divided by the number of non-missing assessments. There will be no imputation of missing data. At least 4 of the 7 measurements need to be recorded for a week to be included in the analysis; otherwise the week will be treated as missing.

Summary statistics of actual values and changes from baseline in weekly average of daily morning ambulatory FEV1 (measured by the handheld spirometry device) at each week through week 36 will be provided by previous double-blind treatment group and for all patients.

FEV1 will additionally be examined for the subgroups defined in Section 3.3.

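### Where the ambulatory FEV1 baseline comes from a withholding day, the weekly changes can carry an upward bronchodilator artefact, because the home readings have no inhaler-timing rule

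*Protocol*

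**What the plan says.** **Clinic readings.** Protocol Table 1, footnote g: "Pre-bronchodilator spirometry assessments at designated clinic visits (weeks 0, 8, and 24, and EOT) should only be performed after withholding short-acting bronchodilators". The interval is at least 6 hours for short-acting agents and at least 12 or 24 hours for long-acting ones. Appendix B repeats this for the clinic spirometry only.

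**Home readings.** Protocol Appendix J asks for an FEV1 and PEF "reading every morning using the handheld spirometer". Protocol 6.1.2 and SAP 6.3.2.1 describe the same daily measurement. None of them says when to blow in relation to an inhaler.

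**Baseline.** Protocol 9.5.2 gives diary-based efficacy variables a mean over the 7 days before the first dose. SAP 4.2.1 keeps that rule for the other diary variables but takes out ambulatory FEV1, "whose baseline value will be derived as outlined in Section 4.2.2". Under SAP 4.2.2 the clinic baseline "will be the last observed value prior to the first dose of reslizumab in this study", and the ambulatory baseline follows the same rule. "For seamless rollovers, baseline will be derived from data collected at the EOT visit of the previous study (30025 or 30027"), and that visit coincides with Visit 1, week 0. For non-seamless rollovers the data come from Visit 1 or before.

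**Follow-up.** SAP 6.3.2.2: "A weekly average of daily morning ambulatory FEV1 (measured by the handheld spirometry device) will be derived using 7-day window intervals", with at least 4 of 7 readings.

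The SAP prevails where the two documents differ. SAP Table 7, which lists changes from the protocol, does not list this one.

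**The concern.** A change from baseline means what it says only if both ends are measured under the same conditions. For seamless rollovers the baseline is tied to a day on which bronchodilators are withheld. The weekly means rest on mornings with no such condition. A patient who inhales on waking and then blows contributes post-bronchodilator follow-up values against a pre-bronchodilator baseline.

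The shift would appear from week 1 and persist. There is no concurrent control, so it would read as improvement on reslizumab in a named secondary efficacy endpoint.

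The planned data could not correct it afterwards. The sample diary asks for a daily puff total, and SAP 6.3.4.1 adds morning and evening counts. Neither records whether an inhaler preceded the reading.

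**Working it through.** The plan has no figure of its own to reproduce: the study is descriptive and its size is not based on power.

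**1. Which weekly means contain a withheld-visit morning?** In SAP Table 1, diary day *d* holds the morning reading of study day *d* + 1. Week *w* covers diary days 7(*w* − 1) + 1 to 7*w*, and the last tabulated diary day is 251. A visit at week *W* falls nominally on study day 7*W* + 1.

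- Week 8: study day 57, diary day 56, in week 8.
- Week 24: study day 169, diary day 168, in week 24.
- Week 36: study day 253, diary day 252, beyond the table.

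So 2 of 251 mornings (0.8%) are withheld-visit mornings, and 36 − 2 = 34 of 36 weekly means contain none. If the week 36 morning were counted, it would be 33 of 36.

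**2. Size of the artefact.** Let *f* be the share of home readings taken after an inhaler and *b* the bronchodilator effect. With a withheld baseline, the artefact in an ordinary week is *f* × *b*. Neither quantity is in the documents. The assumed ranges are *f* = 0 to 0.75 and *b* = 0.05 to 0.20 L.

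| *f* | *b* = 0.05 L | *b* = 0.20 L |
|---|---|---|
| 0 | 0 | 0 |
| 0.25 | 0.0125 L | 0.05 L |
| 0.50 | 0.025 L | 0.10 L |
| 0.75 | 0.0375 L | 0.15 L |

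In weeks 8 and 24, with 7 readings of which one is withheld, multiply by 6/7; the maximum is 0.15 × 6/7 = 0.129 L.

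The yardstick is the 0.129 L FEV1 improvement at week 16 that protocol 5.3.1 quotes for 0.3 mg/kg iv. The range is 0% to 0.15/0.129 = 116% of it.

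These values are for patients with a withheld baseline. In a pooled mean they shrink in proportion to the share of such patients, which the documents do not give.

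**3. What a home-reading baseline would do.** The artefact becomes (*f* after − *f* before) × *b*, which is 0 if inhaler habits do not change. If the Visit 1 morning is withheld and is one of the 7 baseline readings, *f* × *b*/7 remains, at most 0.75 × 0.20/7 = 0.021 L. If habits change, some bias stays: a fall in *f* from 0.50 to 0.25 gives −0.25 × *b*, or −0.0125 to −0.05 L. The baseline rule therefore removes most of the problem, and a record of inhaler timing is needed for the rest.

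**The case against.** A reader might infer that every patient's baseline is a withheld reading and that every weekly change is inflated. The documents do not support that.

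- A non-seamless baseline may be a run-in home reading, taken under the same conditions as follow-up.
- Footnote g governs the hours before the clinic test, not the home blow on the Visit 1 morning. No visit time is given, so a patient seen in the afternoon could use a reliever on waking, blow at home, and still meet the 6-hour rule.
- SAP 4.2.2 does not say whether the seamless ambulatory baseline is the clinic value or that morning's home value. If it is the clinic value, Appendix B adds a change of device, from centralized to handheld spirometry.
- Appendix J is a sample with figures not shown, so a timing prompt on the device cannot be excluded.
- Patients may simply blow first.

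All of this stands, and it limits the point to possible bias in some patients.

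There are also safeguards. The analyses are descriptive. Clinic pre-bronchodilator FEV1 is a separate secondary endpoint with withholding at both ends. FEV1 is shown by previous treatment and by seamless status, so a jump at week 1 in seamless patients already on reslizumab would be a warning. These splits may reveal an artefact, but they cannot separate it from a drug effect.

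Nor is this independent of the single-reading baseline. The mismatch arises largely because the SAP drops the 7-day mean.

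**Conclusion.** The point holds in limited form. It applies to seamless rollovers, and to non-seamless patients whose last pre-dose reading was taken under the Visit 1 withholding rule. For them the SAP compares a single reading from a withholding day with means of home readings for which the readable text gives no bronchodilator-timing rule.

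The possible upward artefact is 0 to 0.15 L in an ordinary week, under the assumed share and effect. It is 0 if patients blow before inhaling. That lower end presumes that no earlier dose is still acting: a reading before the morning inhaler can still fall within 12 or 24 hours of an evening long-acting dose.

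The documents do not show that the bias occurs. They show that the stated rule permits it, at a size that could match the FEV1 improvement quoted in the protocol, and that the planned data could not separate it out.

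**What to change.** 1. **Baseline.** Reconcile SAP 4.2.1 and 4.2.2 with protocol 9.5.2. For all patients, use the mean of the home handheld morning readings over the 7 days before the first dose, with at least 4 of 7 present. For seamless patients, take them from the same 7 parent-study days that SAP 4.2.1 already uses for the other diary variables, and exclude the clinic value. List the rule in SAP Table 7. Confirm first that the parent diaries hold handheld morning FEV1, which these documents do not state.
2. **Timing.** In protocol 6.1.2, Appendix J and the eDiary prompt, ask for the morning reading before the usual morning inhaler. Word it as a measurement-timing request that does not restrict rescue use. Add a yes/no item on whether an inhaler was used before the reading.
3. **Analysis.** Use the item for a supportive summary of readings not preceded by an inhaler. Do not use it to filter seamless baselines: nothing shows that the parent diaries collected it, and a filter could leave those patients without a home baseline.

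The cost is one diary item, one line of instruction and a revised derivation. In the supportive summary, some weeks will fall below 4 of 7 readings.

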4. SELECTION AND WITHDRAWAL OF PATIENTS

Prospective waivers (exceptions) from study inclusion and exclusion criteria to allow patients to be randomized/enrolled are not granted by Teva ([Appendix C](#)).

Study patients will be deemed eligible only if they meet all inclusion criteria and no exclusion criteria are fulfilled. Patients who are currently enrolled in Studies 30025 and 30027 will be required to complete their respective treatment periods to be eligible for this study. In addition, adolescents (patients 12 through <18 years of age) from Study 30025 must also complete the 12-week early follow-up visit (off study drug) before transferring to this OL study.

4.1. Patient Inclusion Criteria

Patients may be included in the study only if they meet all of the following criteria:

- a. Written informed consent is obtained. A patient 12 through <18 years of age must provide assent, and their parent(s) or legal guardian(s) must provide consent.
- b. Male or female patient 12 years or older with eosinophilic asthma who was previously randomized and completed the treatment period in either of the double-blind, placebo-controlled studies (Study 30025 or 30027) for sc reslizumab and who by the assessment of the Principal Investigator can safely participate in this study. Adolescents from Study 30025 must also complete the early follow-up visit before being eligible for this study.
- c. Unless surgically sterile or postmenopausal, female patients must have a negative urine pregnancy test at baseline. Definitions of sterile and postmenopausal are given in [Appendix E](#).
- d. Females of childbearing potential (not surgically sterile or postmenopausal) must have an exclusively same-sex partner or use a medically acceptable method of contraception and must agree to continue the use of this method for the duration of the study and for 5 months after discontinuation of the study drug. Acceptable methods of contraception include intrauterine device, steroid contraceptive (oral, implanted, transdermal, or injected), barrier method with spermicide, abstinence, bilateral tubal occlusion, and partner vasectomy.
- e. The patient must be willing and able to comply with study restrictions and willing to return to the investigational center for the follow-up procedures and assessments as specified in this protocol.

4.2. Patient Exclusion Criteria

Patients will be excluded from participating in this study if they meet any of the following criteria:

- a. Patient has received any iv or sc reslizumab administration in any previous clinical trial other than Studies 30025 and 30027.
- b. Patient withdrew early (discontinued from treatment) from either of the placebo-controlled reslizumab studies, Studies 30025 and 30027, for any reason.
- c. The patient has any clinically significant, uncontrolled medical condition (treated or untreated) that would interfere with the study schedule or procedures and interpretation of efficacy results or would compromise the patient's safety.
- d. The patient has another confounding underlying lung disorder (eg, chronic obstructive pulmonary disease, interstitial lung disease, bronchiectasis eosinophilic granulomatosis with polyangiitis [also known as Churg-Strauss syndrome], or allergic bronchopulmonary aspergillosis).
- e. The patient has a known/diagnosed hypereosinophilic syndrome.
- f. The patient has a diagnosis of malignancy within 5 years of the screening visit, except for treated and cured non-melanoma skin cancers.
- g. The patient is a pregnant or lactating woman or intends to become pregnant during the study or within 5 months after the last dose of study drug. Administration of IMP will be discontinued for any female patient who becomes pregnant during the study.
- h. The patient required treatment for an asthma exacerbation within 4 weeks of screening or during the screening. (Note: This is required only in patients who did not rollover seamlessly from Study 30025 or 30027, ie, had a gap between placebo-controlled study EOT and screening for Study 30066 [including adolescents from Study 30025 who must also complete the early follow-up visit].)

Patients who did not rollover seamlessly from Study 30025 or 30027 may be considered for rescreening if they are excluded from study participation for not satisfying this criterion. A patient may be rescreened for this reason 1 time only. The duration between the first visit during the screening period and the rescreening must be >30 days.

- i. The patient is a current smoker (ie, has smoked within the last 6 months before screening) or has a smoking history ≥ 10 pack-years.
- j. The patient is currently using any systemic immunosuppressive or immunomodulatory biologic (eg, anti-immunoglobulin E mAb or other mAb [eg, mepolizumab, benralizumab, dupilumab] or soluble receptors) or non-biologic (eg, methotrexate or cyclosporine), except maintenance oral corticosteroids, for the treatment of asthma (up to and including 40 mg of prednisone daily or equivalent every-other-day dosing). Note: Previous use of such agents that occurred >5 half-lives from the initial screening visit may be allowed.

- k. The patient participated in a clinical study other than approved Teva reslizumab studies within 30 days or 5 half-lives of the investigational drug before screening, whichever is longer.
- l. The patient has a history of an immunodeficiency disorder, including human immunodeficiency virus (HIV).
- m. The patient has current or suspected drug and/or alcohol abuse.
- n. The patient has an active helminthic parasitic infection or was treated for one within 6 months of screening.
- o. The patient has a history of allergic reaction or hypersensitivity to any component of the study drug.
- p. The patient is expected to be poorly compliant with study procedures or visits.
- q. The patient is a vulnerable patient (eg, a patient who is or may be for any reason unable to take care of him or herself, unable to protect him or herself against significant harm or exploitation, or kept in detention).

